The primary outcome for Aim 2 is the Bayley Developmental Quotient (DQ) measured at 2 years of age. The average score across the two IV iron arms will be compared to the oral arm at the alpha=0.05 level. We expect to obtain data for approximately 85% of consented participants at this time point for a sample of at least 147 per arm. This sample size gives more than 90% power to detect a difference in means of 5 units on the BSID mean score assuming a standard deviation of 15 at the alpha=0.05 level. Because effect sizes in the range of 5 to 7.5 are generally clinically meaningful for the BSID, the study is well powered to detect clinically meaningful differences.

Primary Data Analysis

Statistical analyses involve both formal hypotheses testing for specified primary outcome measures and supportive descriptive analyses of secondary outcome measures.

Hemoglobin and log transformed ferritin will be separately modeled using mixed effects linear regression. Both outcomes will be measured at birth and 4 months, and hemoglobin will also be measured at 12 months. The mixed effects models will treat time as a categorical value and include fixed effects for time, treatment, and time by treatment interaction. Correlation among repeated measurements for each subject will be modeled through structuring the variance-covariance matrix of the residuals. Inclusion of the time by treatment interaction will allow for estimation of mean iron indices at each measurement time for each group. Within these models, the primary hypothesis tests for aim 1 will be performed by comparing the average across the two IV iron groups to the oral iron group with respect to the mean values at birth and at 4 months using a significance level of 0.025.

A similar mixed-effects model will be used for modeling Bayley DQ cognitive domain in participating children at 2 and 3 years of age. The primary test for aim 2 will be performed by comparing the average across the two IV arms to the oral iron arm at 2 years using a significance level of 0.05.

Secondary Analyses

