An analysis of maternal hematologic indices will be completed when all women have passed the 12 month collection period. This analysis will include all available maternal blood data through 12 months. Based on the results of this analysis, the research team may decide to suspend collection of maternal blood at 24 months. Other extensive interim analysis is not planned. However, typical study monitoring activities could trigger such an analysis for one or more of the following reasons: recruitment proves problematic, making it difficult to perform an adequate number of tests and obtain measurements at desired time points; study withdrawals, investigator-recommended discontinuations, or 'loss-to-follow-up' among children enrolled in the study are significant; and/or there is a poor ratio for data obtained vs. data expected for important study variables. If undertaken, the interim analysis would consider if continuation

of the study, despite existence of challenges such as those mentioned, could nevertheless provide enough valid evidence to judge whether the primary study hypotheses remain valid. If the answer is no, the study could be prematurely stopped.

Safety Analyses

All safety analyses will be descriptive based on the safety cohort with no planned formal inference for safety. All adverse events will be summarized by system organ class by arm with point and interval estimates of the risk of each of these events estimated by either exact binomial methods or normal approximations to the binomial as appropriate for the incidence of the event.

Descriptive statistics will also be generated for maternal and infant mortality and for incidence of serious adverse events (SAEs).

Analysis Cohorts

Intent-to-treat (ITT) cohort: study participants (mothers or infants, depending on the particular analysis) will be included using group assignments for the mother as randomized.

Delivery iron status cohort: Analyses that examine outcomes as a function of delivery iron status will include enrolled maternal participants with sufficient delivery data to determine iron status of the infant at delivery.

Assignment of participants into the various cohorts will be determined based on a masked data review prior to initiation of analysis.

F. Gender/Minority/Pediatric Inclusion for Research

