This *RAPIDIRON-KIDS Study* involves no intervention, and thus the risks associated with study participation can be considered minimal but include the possibility that drawing blood for analysis could cause bruising and, rarely, infection. No serious risks are associated with the various assessments indicated in Table 1, although some discomfort or anxiety on the part of the child or a mother cannot be ruled out but can often be ameliorated by individuals appropriately trained to conduct assessments.

5. Procedures for Protecting Against or Minimizing Potential Risks

Care will be taken to reduce the risk of bruising. Sterile technique will be utilized during blood draw to reduce risk of infection. Personnel conducting sociodemographic, neurodevelopmental, and other assessments will have adequate background and relevant training to ensure competency.

6. Potential Benefits, Importance to Participants and Others

The possible benefits to participants may be earlier diagnosis of iron deficiency due to a screening schedule which encompasses more monitoring opportunities than is associated with usual practice. Both mothers and infants whose hemoglobin values fall below a pre-designated cutoff will be appropriately referred as per standard of care. Further, if neurodevelopmental testing indicate possible disorder, parents will be told about resources for confirming a diagnosis and for seeking supportive services (if they exist locally).

In combination with the parent study, the *RAPIDIRON Trial*, it is hoped that this follow-up study will result in the expanded use of a more effective approach for the treatment of IDA and decrease the risk that offspring will suffer the consequences of an ineffective IDA treatment approach. Further, if the IV iron treatment approach is determined feasible and adopted widely as a frontline treatment for IDA in pregnancy, the number of future beneficiaries of these studies can be multiplied.

7. Discussion of Why Risks are Reasonable in Relation to Benefits

The *RAPIDIRON-KIDS Study* can be considered an observational study with minimal risk. However, if the study results in earlier diagnosis and earlier treatment of iron deficiency, and delivery of services to address developmental disorders, then participating children and mothers may receive greater benefit than would be the case if such problems were recognized later in life.

H. Data and Safety Monitoring Plan

1. Data and Safety Monitoring Plan (DSMP)

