For the *RAPIDIRON-KIDS Study*, a serious adverse event (SAE) involves mothers (and their infants) who were treated for iron deficiency anemia as participants in the *RAPIDIRON Trial* and who provide consent for themselves and their offspring to participate in the *RAPIDIRON-KIDS Study*. To qualify as an SAE, the event must fulfill at least one of the criteria below:

- Results in a maternal or neonatal death, or fetal death >20 weeks gestation;
- Is life-threatening;
- Requires an unanticipated hospitalization or prolongs an existing hospitalization
- Results in persistent or significant disability or incapacity; or
- Represents other serious or unexpected adverse events that a study investigator feels should be reported, including need for resuscitation.

Specific forms will be utilized to report an SAE. For an SAE, the reporting form should be sent to the person designated to receive it within 7 days of the notification of the event. Reportable adverse and serious adverse events will be shared with the DSMB. If there is an unanticipated problem recognized as posing a risk to participants or others and it is likely to reoccur, a designated researcher should obtain additional information on the unanticipated event and compile a report to forward to the study Principal Investigator, Chief Quality and Safety Officer, and the Chair of the DSMB. The Chair will review the report and determine significance of the event to the study and the need for action to avoid harm to participants. The Chair may put the report on the agenda of the next DSMB meeting or communicate with members to address the unanticipated problem sooner.

At each scheduled DSMB meeting after completion of the primary randomized trial, SAE data and a report summarizing retention and participant status will be prepared for review and discussion. Following its deliberations, the DSMB will issue any recommendations it may have and specify that the study should continue based upon absence of safety concerns or concerns about data quality or excessive loss-to-follow-up.

2. Data and Safety Monitoring Board (DSMB)

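### The safety analysis plans simple binomial risks of all adverse events in an undefined cohort, although follow-up can be incomplete over 36 months and no collection of non-serious events is described

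*Combined protocol and SAP*

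**What the plan says.** Section E, Safety Analyses, sets the population and the inferential status: "All safety analyses will be descriptive based on the safety cohort with no planned formal inference for safety". It then sets the content, "All adverse events will be summarized by system organ class by arm with point and interval estimates of the risk of each of these events", and the estimator, "estimated by either exact binomial methods or normal approximations to the binomial as appropriate for the incidence of the event". A further sentence adds descriptive statistics for maternal and infant mortality and for SAE incidence.

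Analysis Cohorts, directly below, has two entries. The first is "Intent-to-treat (ITT) cohort: study participants (mothers or infants, depending on the particular analysis) will be included using group assignments for the mother as randomized". The second begins "Delivery iron status cohort: Analyses that examine outcomes as a function of delivery iron status will include enrolled maternal participants". A closing sentence leaves assignment to cohorts to a masked data review. No safety cohort is defined.

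On collection, section H.1 defines an SAE, sets a 7-day reporting time and says "Specific forms will be utilized to report an SAE". It also mentions reportable adverse events that go to the monitoring board, without defining them. Section G.2 lists maternal hospitalization and transfusion among the data collected, and section D lists offspring hospitalizations over the first three years as a secondary outcome. Section G.2 also refers to general data forms but describes no adverse-event content. Section G.4 names the physical risk of the study's own procedures: "drawing blood for analysis could cause bruising and, rarely, infection".

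**The concern.** Three parts of the safety plan do not connect.

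- **Events.** The table promises all adverse events by system organ class. No definition, elicitation schedule, collection window or coding dictionary is given for non-serious events. A proportion built on events that were not systematically sought cannot be read as a risk.
- **Population.** In a study of mother-child dyads, an undefined safety cohort leaves open whether the unit is the mother or the child and when the period at risk begins. Women may consent from the 26-30 week visit until delivery, and a fetal death after 20 weeks is an SAE, so the starting point matters.
- **Estimator.** Hospitalizations are followed for three years. A binomial proportion gives each person in the denominator the same weight, however long she or the child was observed. Loss to follow-up appears in the statistical section only as a possible trigger for an interim analysis.

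Section A makes promotion of wider IV iron use conditional on the absence of safety concerns, so the by-arm risks will be read even though they are descriptive. If loss differs between arms, the proportions could show a difference that is not there, or mask one that is.

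**Working it through.** **What the documents supply.** The safety section states no figure. The nearest number is in Sample Size (Aim 2): "We expect to obtain data for approximately 85% of consented participants at this time point". It reproduces: 175 × 0.85 = 148.75 per arm, against the stated minimum of 147. This is availability of Bayley data at 24 months, not a dropout rate. No retention figure is given for 36 months.

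**Assumptions, none from the documents.** True 36-month risk of a first event R = 15%. Total loss by 36 months d between 5% and 21.6%. The upper end comes from reading the 15% without Bayley data as pure loss and extending it at a constant rate: 1 − 0.85^(36/24) = 0.216. Event and loss hazards are constant and independent.

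**Formulas.** With a = −ln(1 − R) and c = −ln(1 − d), both over 36 months:

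- Full-cohort proportion: F = a/(a + c) × [1 − (1 − R)(1 − d)]
- Known-status proportion (events plus event-free completers): K = F / [F + (1 − R)(1 − d)]

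**Results for R = 15% (a = 0.1625).**

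| Total loss d | c | (1 − R)(1 − d) | F | K |
|---|---|---|---|---|
| 5% | 0.0513 | 0.8075 | 14.6% | 15.3% |
| 15% | 0.1625 | 0.7225 | 13.9% | 16.1% |
| 21.6% | 0.2438 | 0.6661 | 13.4% | 16.7% |

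Example at d = 15%: F = 0.5 × (1 − 0.7225) = 0.1388, and K = 0.1388/(0.1388 + 0.7225) = 0.161.

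In relative terms F is about 2% to 11% too low and K about 2% to 11% too high. The direction depends on a denominator that the plan does not state.

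**Loss that differs by arm (assumed 10% against 25% by 36 months, same true 15%).**

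- F: 0.1625/0.2679 × (1 − 0.765) = 14.3%, against 0.1625/0.4502 × (1 − 0.6375) = 13.1%. The false gap is 1.2 points.
- K: 0.1426/(0.1426 + 0.765) = 15.7%, against 0.1309/(0.1309 + 0.6375) = 17.0%. The false gap is 1.3 points in the opposite direction.

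**Scale.** The standard error of a 15% risk with about 175 per arm is √(0.15 × 0.85/175) = 2.7 points. For IV arms combined against oral (350 against 175) it is √(0.1275/350 + 0.1275/175) = 3.3 points. The bias is smaller than the sampling error, but it is systematic and avoidable.

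**The case against.** The case for leaving the text alone has weight.

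- **No rule for dropouts is stated.** A reader might infer that families lost to follow-up would be counted as event-free and that every risk would therefore be too low. The documents do not say so. They name a binomial method and no denominator, and a known-status denominator biases the other way. What stands is that neither denominator handles unequal follow-up.
- **The 85% is not retention.** A reader might infer 15% dropout by 24 months. Consent precedes delivery, and the sample-size text explains the extra recruitment by stillbirth, neonatal death and unusable cord blood. The same 85% is used at birth. Part of the shortfall may therefore be events rather than silent loss. A child without a Bayley score may also still have hospitalization data.
- **Other adverse events may be recorded.** A reader might infer that the table could hold only SAEs. Section H.1 mentions reportable adverse events and section G.2 mentions general data forms, so that is not established. What stands is that no collection procedure for them is described.
- **The cohort gap may matter little.** All participants were randomized and treated in the parent trial, so the usual distinction between randomized and treated populations largely disappears. The choice of mother or child, and the start of the risk period, remain open.
- **The stakes are limited.** The infusion is given at 14-17 weeks, before consent to this study, so acute drug safety belongs to the parent trial. Mortality and SAE incidence are promised separately and do not depend on the all-events table. This argument stands and limits the severity.

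**Conclusion.** The concern holds as a minor point. The plan promises by-arm risks of all adverse events in a safety cohort that it names but does not define, and it describes collection only of SAEs, hospitalizations and transfusions. Its estimator ignores follow-up time. Under the stated assumptions a true 36-month risk of 15% would read as 13.4% to 14.6% or as 15.3% to 16.7%, depending on the denominator, and assumed loss of 10% against 25% would produce a false gap of just over one percentage point. Events concentrated early in follow-up would make these errors smaller. Loss related to the event itself would change them in a way this calculation does not cover. The documents do not support the stronger claim of a known downward bias of a given size. Because safety is descriptive and the study gives no intervention, no primary conclusion is at risk.

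**What to change.** Amend Safety Analyses and Analysis Cohorts in section E as follows.

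1. **Events.** Limit the by-arm table to what the study describes collecting: SAEs, deaths, hospitalizations and transfusions. Alternatively, describe how and when other adverse events are elicited and coded. List deaths separately, since the SAE criteria name maternal, neonatal and fetal death while the analysis promises infant mortality; the two sections should be reconciled.
2. **Denominators.** Replace the safety cohort with two stated populations, each by the mother's randomized arm: all consented mothers from consent, with fetal deaths counted here, and all live-born enrolled children from birth.
3. **Estimator.** Estimate 36-month risk by cumulative incidence with 95% intervals, censoring at last contact and treating death as a competing event for non-fatal events. Keep exact binomial intervals for windows in which everyone is fully observed.

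The cost is SAP wording and standard survival code, with no new visits. Intervals will be slightly wider and fewer event categories will be tabulated. A question about bruising or infection after blood draws could be added at existing visits, but that is optional.
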